4.4.3 Safety Analysis Set

The Safety Analysis Set (SAF) will include all subjects who have received at least one dose of study drug. The SAF will be used for safety analysis.

If a subject received incorrect study drug, i.e., study drug different to the one assigned per the randomization list, the subject will be summarized and analyzed for the study drug actually received.

4.4.4 Pharmacokinetic Analysis Set

The PK Analysis Set (PKS) will include all randomized subjects in the PK and pharmacodynamic subset who have at least one available pre-dose sample and one quantifiable study drug concentration after initiation of treatment. Subjects are included in the PK and pharmacodynamic subset if they consented and participated in the PK and pharmacodynamic evaluations.

4.4.5 Pharmacodynamic Analysis Set

The Pharmacodynamic Analysis Set (PDS) will include all subjects in the PK and pharmacodynamic subset and sampled for pharmacodynamics who have at least an available pre-dose pharmacodynamic sample and an available pharmacodynamic sample obtained after the administration of the first dose of rituximab has started. Subjects are included in the PK and pharmacodynamic subset if they consented and participated in the PK and pharmacodynamic evaluations.

Subject evaluability for specific pharmacodynamic parameters will be decided under blinded conditions.

4.4.6 Immunogenicity Analysis Set

All randomized subjects with at least one immunogenicity sample with a valid result will be included in the Immunogenicity Analysis Set.

4.4.7 eCRF CCI Risk Category Analysis Set

The eCRF CCI Risk Category Analysis Set will include all subjects from the ITT Analysis Set but with study treatment received (even if different from the randomized study treatment) and CCI risk category as per eCRF (even if different from the category used in the stratified randomization).

4.4.8 eCRF Tumor Grade Analysis Set

The eCRF Tumor Grade Analysis Set will include all subjects from the ITT Analysis Set but with study treatment received (even if different from the randomized study treatment) and tumor grade as per eCRF (even if different from the category used in the stratified randomization).

4.4.9 Analysis Set Summaries

Analysis sets will be summarized and listed for the ITT Analysis Set by:

• Summary of number and percentage of subjects in the respective analysis set, by treatment group and overall

CCI	CONFIDENTIAL	Project Document Version No. 4.0
Effective Date: 26 Nov 19	Project Docu	ment Effective Date: Date of last signature
CCI		Page 20 of 65

[name] S.A	
Protocol RI-01-006	Statistical Analysis Plan

• By-subject listing including treatment group, center, subject identifier, inclusion/exclusion flag for each analysis set and reason for exclusion from an analysis set, if applicable.

4.5 **Protocol Deviations**

Major protocol deviations are defined as those deviations from the protocol likely to have an impact on the subject's rights, safety, well-being, and/or the primary efficacy endpoint BOR up to Week 28.

Subjects with major protocol deviations (defined below) will be excluded from the PPS. Please refer to the study protocol deviation specification for more information.

A summary of the number and percentage of subjects with protocol deviations by protocol deviations classification (minor or major), will be provided by treatment group for the ITT Analysis Set. Protocol deviations related to the COVID-19 pandemic will be summarized for the ITT Analysis Set.

A by-subject listing will be provided including subject identifier, protocol deviation classification, protocol deviation description and exclusion from specific analysis sets. Protocol deviations related to the COVID-19 pandemic will be presented in a separate listing.

4.6 Study Subjects

4.6.1 Disposition of Subjects

The disposition of all subjects who enter the study will be provided, from enrolment to study completion. The subject disposition summaries include the following (overall and by treatment group where applicable) summaries based on associated analysis sets:

4.6.1.1 Subjects Screened

A summary of the number of subjects screened with the number and percentage of screen failures and reasons for screen failure.

4.6.1.2 Subjects Randomized

A summary of number of subjects who satisfied eligibility criteria for enrolment and were randomized to one of the two study treatment groups.

4.6.1.3 Subjects Treated

The number of subjects who received treatment, completed Week 12, Week 28, completed study and discontinued from study along with primary reason of discontinuation from study will be summarized and listed.

The similar summary for subject disposition will be performed by stratification factors: CCL risk category, tumor grade, geographical area as well as by, treatment group and overall.

A separate summary of subject's disposition by treatment period will also be provided. This display will show the number of subjects who initiated induction treatment, completed induction treatment period, completed induction period and started maintenance treatment period, who initiated maintenance treatment, completed maintenance treatment period, entered follow up, completed follow-up, and who discontinued from induction/ between induction period completion and starting of maintenance treatment period /maintenance treatment/, the primary reasons of discontinuation including disease progression, adverse events, death, subject withdrew consent, lost to follow-up, investigator's decision, COVID-19 or related symptoms and other reasons will be summarized by treatment group and overall.

[name] S.A Protocol RI-01-006

4.6.1.4 Subjects per Analysis Set

A summary of the number of subjects per analysis set will be provided (see Section 4.4 for definition of analysis sets).

A by-subject listing of subject disposition will be generated that includes start/end date of screening, randomization, screening failure date, reason of screening failure, subject's received treatment, completion / early termination of treatment date, completion of study / early termination of study date, along with primary reason for early termination. A separate listing of subject disposition will be provided which includes induction treatment, maintenance treatment and follow-up along with primary reasons for early termination, if any.

4.7 Demographic and Other Baseline Characteristics

All demographic summaries will be produced for the ITT Analysis Set.

Demographic and baseline characteristics (see Sections 4.7.1 and 4.7.2) measured before randomization will be listed by subject and summarized by treatment group and overall, for the ITT Analysis Set.

4.7.1 Demographics Characteristics

- Age (years)
- Age group: $< 60, \ge 60$ years
- Gender: Male, Female
- Height and weight as per IVRS
- Ethnicity: Hispanic or Latino, Not Hispanic or Latino, White, Black, Asian, Multiracial, Native, Not Reported, Unknown
- Race: White, Asian, Black or African American, American Indian or Alaska Native, Aboriginal/Torres Strait Islander, Native Hawaiian or Other Pacific Islander, Unknown, Not reported, Other
- BSA(m²) as per eCRF.
- Geographical Region: USA, Europe, Asia Pacific.

Note: BSA may be calculated by any of the below derivation methods.

Mosteller⁵ formula:

$$BSA[m^{2}] = \sqrt{\frac{\text{Height}[cm] \times \text{Weight}[kg]}{3600}}$$

Du Bois⁶ formula:

 $BSA[m^2] = 0.007184 \times Height[cm]^{0.725} \times Weight[kg]^{0.425}$

Haycock⁷ formula:

 $BSA[m^2] = Weight[kg]^{0.5378} \times Height[cm]^{0.3964} \times 0.024265.$

4.7.2 Other Baseline Characteristics

Other baseline characteristics are:

• Eastern cooperative oncology group (ECOG) performance status: $0, 1, \ge 2$

CCI	
Effective Date: 26 Nov	19
CCI	

[name] S.A Protocol RI-01-006

- Serum beta-2 microglobulin: normal, above upper limit of normal
- Hemoglobin level: $\geq 120 \text{ g/L}$, < 120 g/L
- Bone marrow involvement: absent, present

•	CCI	

- Histological Tumor Grade for FL: grade 1, grade 2, grade 3a
- Histological Tumor Grade for FL as per randomization stratum: grade 1 or 2, grade 3a.

4.7.3 Social and Economic Factors

Baseline social and economic factors will be listed. These factors include educational qualification, occupation, income, family history of allergy related to cancer, alcohol ever consumed, amount of beer consumed, frequency of beer consumed, amount of wine consumed, frequency of wine consumed, amount of spirits consumed, frequency of spirit consumed, any drug abuse, drug usage, and frequency of drug usage.

The by-subject listings will also include additional information provided for these factors such as amount of beer consumed, start of date of drug usage etc.

4.7.4 Follicular Lymphoma Staging

Follicular lymphoma staging will be listed by subject and summarized by treatment group and overall. The number and percentage of subjects will be provided for the following:

- Disease diagnosis histologically confirmed,
- Ann Arbor staging
- CCI

The by-subject listings will also include additional information provided for these factors such as date of histological conformation etc.

4.7.5 Disease Diagnosis

Disease diagnosis will be listed by subject and summarized by treatment group and overall. The number and percentage of subjects will be provided for: Time since initial diagnosis, time since histological confirmation, scan type/modality, CD20 positivity confirmation, current site of disease, disease confirmation by bone marrow biopsy, histological confirmation, any prior anti-cancer therapy, any surgery related to current cancer and any prior radiotherapy for current cancer.

In addition to above, the by-subject listings will also include date of initial diagnosis, scan type/modality, date of biopsy and date of histological confirmation.

4.7.6 Medical and Surgical History including medications

Medical conditions will be coded by the Medical Dictionary for Regulatory Activities (MedDRA). The final MedDRA version to be used will be decided prior to database lock (for both primary and final analysis).

[name] S.A	
Protocol RI-01-006	

Medical and surgical history/conditions present at screening will be summarized and listed. They will be summarized by MedDRA primary System Organ Class (SOC) and Preferred Term (PT). Verbatim recorded history/conditions will be listed together with the coded terms, date of diagnosis/surgery and whether the condition was ongoing at the time of first study drug administration. The number and percentage of subjects with each medical condition will be provided by treatment group for the SAF.

4.8 **Prior and Current Concomitant Medication**

All medications taken by a subject within one month prior to screening are regarded as prior medications and must be documented as such in the eCRF. All medications still being taken by a subject at the time of signing the Informed Consent Form (ICF) and which continue to be taken during the study, as well as all medications started after signing of the ICF, are regarded as concomitant medications and must be documented as such in the eCRF. Imputation of partial dates for prior and concomitant medication is described in Appendix 2 Partial Date Conventions.

A summary of the number of subjects with prior and current concomitant medications by treatment group and overall will be generated for the SAF. The number (n) and percentage will be provided by Anatomical Therapeutic Chemistry (ATC) term, PT by World Health Organization - Drug Dictionary Enhanced (WHO-DDE) version SEP2020 B3 and each subject will be counted once only under each category. A similar summary table for prior and current concomitant medications taken due to COVID-19 for the SAF will also be presented.

A by-subject listing of prior/current concomitant medication will be generated using the SAF, including start/end date of medication taken, dose information (dose name, unit, total dose, route and frequency), indication /reason for treatments, and any anti-cancer therapies/ radiotherapies/ surgeries taken during the study. Prior and concomitant medications taken due to COVID-19 will be presented in a separate listing.

4.9 Treatment Compliance

Study treatment compliance will be calculated as follows and will be summarized for the SAF:

study treatment compliance(%) = $\frac{\text{total dose administered (mg)}}{\text{total intended dose (mg)}} \times 100$

For subjects with early study treatment discontinuation, dose intended and administered, respectively, up to the study treatment discontinuation will be considered for compliance calculation.

A summary of treatment compliance by treatment group and visit (including the number and percentage of compliant and non-compliant subjects) will be provided for induction period and maintenance period. Compliant subjects are those subjects who had 95% to 105% study treatment compliance, otherwise subjects will be considered non-compliant.

A by-subject listing of study drug infusion including starting and end date and time, visit, intended dose, actual dose administered, volume administered, body surface area, dose delay, missed dose, reason for interruption or discontinuation, rate of infusion, duration of infusion, reason for interruption or discontinuation during infusion, kit allocation date, kit number and AE details that lead to interruption or discontinuation will also be provided.

[name] S.A Protocol RI-01-006

4.10 Efficacy Analyses

4.10.1 Analysis and Data Conventions

4.10.1.1 Multi-center Studies

For the following sections of safety and efficacy analysis, the term 'Center' in this SAP will be defined as investigator site.

Data from participating centers will be pooled prior to analysis. However, summary of randomized subjects by geographical region and investigator sites (if available) will be provided.

4.10.1.2 Adjustments for Covariates

No covariate adjustment is planned in the primary efficacy endpoint main analysis.

Stratification variables used in the stratified randomization will be included in stratified analyses of the primary efficacy endpoint as a part of sensitivity analysis.

4.10.1.3 Handling of Missing Data

Various approaches will be applied to handle missing data; main, sensitivity and supportive analyses will be performed to explore the robustness of statistical results for the primary efficacy endpoint, see Sections 4.10.2.2.3 to 4.10.2.3.

Analysis and descriptive summaries for other endpoints will be based on available observed data.

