4.5 End of Study Definition

Subjects who complete the study or subjects who discontinue from the study early will attend an EOS/ET Visit. Subjects experiencing disease progression will discontinue study drug and attend the ET Visit, which is to be scheduled 8 weeks after the last dose of study drug administration. These subjects will then be contacted by telephone for information on survival, AEs, and concomitant medications (Section 4.5.1) every 8 weeks, for a total observation period of 52 weeks (Section 4.5.1). Subjects discontinued from study drug due to a reason other than disease progression will also attend the ET Visit scheduled 8 weeks after the last dose of study drug, and then will continue to attend scheduled tumour assessments (at which AE and concomitant medication information will also be collected) up to disease progression or Week 52, whichever occurs first, as described in Section 4.1.1.

End of Study/Early Termination assessments are as follows:

- 1. Clinical assessments will include the following: Physical examination (including weight), vital signs measurement (blood pressure, heart rate, respiration rate, and oral, axillary, or tympanic body temperature).
- 2. Serum pregnancy test (human chorionic gonadotropin [hCG]) for women of childbearing potential. Female subjects with documented history of hysterectomy, bilateral oophorectomy, medically confirmed ovarian failure, or screening follicle stimulating hormone (FSH) test demonstrating post-menopausal status are exempted from pregnancy testing.
- 3. ECOG performance status assessments.
- 4. Clinical laboratory tests: Blood and urine samples will be taken for haematology, coagulation, biochemistry, and urinalysis.
- 5. Serum LDH and β -2 microglobulin evaluation.
- 6. 12-lead ECG (local ECG equipment with ECG to be read locally by a medically qualified and experienced ECG reader at the study site).
- 7. Viral disease screening at the EOS Visit.
- 8. Tumour assessments (using a computed tomography [CT] scan and, where available according to study site standard of care, a fluorine-18-fluorodeoxyglucose positron emission tomography [[¹⁸F] FDG-PET] or PET-CT scan) based on central radiology review in accordance with the response criteria for malignant lymphoma.¹³
- 9. Samples for BAb and NAb will be obtained.

- 10. A pharmacodynamic sample will be obtained only in the subjects undergoing PK and pharmacodynamic assessments.

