7.2 Subject Discontinuation/Withdrawal from the Study

Subjects may withdraw from the study at any time at their own request, or they may be withdrawn at any time at the discretion of the Investigator or Sponsor/designee for safety, behavioural, or administrative reasons, or the inability of the subject to comply with the protocol required schedule of study visits or procedures at a given study site.

The decision to withdraw consent and discontinue participation in the study will not prejudice the subject's future medical treatment in any way. If a subject does not return for a scheduled visit or is lost to follow-up, every effort will be made to contact the subject. All attempts to contact the subject and information received during contact attempts must be documented in the subject's medical record. In any circumstance, every effort will be made to document subject outcome, if possible. The Investigator should inquire about the reason for withdrawal and request the subject to return for the EOS/ET (Week 52) Visit, if applicable, and follow-up with the subject regarding any unresolved AEs. The Investigator or sub-investigator will be responsible for reporting subject withdrawal to the Sponsor/designee. Subjects who withdraw after randomisation are not to be replaced and their randomisation number will not be re-used. If these subjects subsequently experience disease progression, then they will continue to be followed up as described in Section 4.1.1.

If a subject withdraws from the study, and also withdraws consent for disclosure of future information, no additional data should be collected. The Sponsor/designee may retain and continue to use any data collected before such withdrawal of consent.

Subjects shall be withdrawn during the course of the study when subject well-being is at risk, including but not limited to:

- Unacceptable AE.
- Subject is confirmed to be pregnant.

Subjects who experience disease progression in accordance with published response criteria for malignant lymphoma ¹³ (per Investigator assessment) are expected to be withdrawn from study drug, to attend the ET Visit, and to be followed up by telephone for survival as described in Section 4.1.1. Subjects who wish to remain in the study but withdraw from the study drug for any reason other than disease progression will return for an ET Visit and continue to attend scheduled tumour assessments up to disease progression or Week 52, whichever occurs first.

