- 2. Clinical assessments will include the following: Physical examination (at the discretion of the Investigator), vital signs measurement (seated blood pressure, heart rate, respiration rate, and oral, axillary, or tympanic body temperature).
- 3. ECOG performance status.
- 4. Clinical laboratory tests: Blood and urine samples will be taken for haematology, biochemistry, coagulation, urinalysis, and pregnancy tests.

- 5. Serum LDH and β -2 microglobulin evaluation.
- 6. Samples for BAb and NAb will be obtained.
- 7. Assess AEs.
- 8. Review concomitant medications.

Maintenance Treatment Period (Week 12 to Week 36 ± 7 days)

Subjects will attend the study visit at Week 12 ± 7 days, and thereafter every 8 weeks (± 7 days) until Week 36. The subjects will attend the study site preferably from the morning until approximately mid-afternoon.

The procedures and assessments for the Maintenance Treatment Period are as follows:

- 1. Completion of a COVID-19 related screening questionnaire.
- 2. Clinical assessments will include the following: Physical examination (at the discretion of the Investigator, but including weight), vital signs measurement (blood pressure, heart rate, respiration rate, and oral, axillary, or tympanic body temperature).
- 3. ECOG performance status assessments.
- 4. Urine or serum pregnancy test (performed locally, according to local practice).
- 5. Clinical laboratory tests: Blood and urine samples will be taken for haematology, biochemistry, coagulation, and urinalysis.
- 6. At Week 28 Only: Samples for BAb and NAb will be obtained before the infusion of study drug.
- 7. Serum LDH and β -2 microglobulin evaluation.
- 8. Viral disease screening: HBV DNA (as applicable) and HCV RNA (as applicable).
- 9. At Week 12 and 28 only (Month 3 and Month 7, i.e. 2 and 6 months after completion of rituximab induction) tumour assessments (using a CT scan and, where available according to study site standard of care, a [¹⁸F]FDG-PET or PET-CT scan) based on central radiology review in accordance with the response criteria for malignant lymphoma.¹³ Subjects who have withdrawn from study drug for any reason other than disease progression will also undergo tumour assessment at Week 28.

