9.1.2 Missing Data

Imputation of missing data in the primary efficacy analysis is described in Section 9.4.1.1 Partial dates for start or stop date of AEs will be imputed in an appropriately conservative way. Detailed methods for handling missing data will be given in the SAP. For substantial missing assessments due to the COVID-19 pandemic additional sensitivity analyses will be performed to determine if there was an impact on the efficacy endpoints. Methods for handling missing data should outline the assumptions utilized and discuss if this method of choice may have an effect on the estimate of the treatment effect.

Other missing values will not be imputed, unless otherwise specified in each analysis section.

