4.2.2 General Categorical Data Presentation

Categorical data will be summarized in terms of the number of subjects providing data at the relevant time point (n), frequency counts and percentages.

Percentages will be presented to one decimal place. Percentages will be calculated using 'n' (the total number of subjects providing data at the relevant time point) as the denominator.

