4.10.3 Analysis of Secondary Efficacy Endpoints / Variables

Definitions of secondary efficacy endpoints / variables are found in Section 3.2.1.2; they will be analyzed for the ITT Analysis Set.

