4.10.3.1 Analysis of Progression Free Survival by Central Review

PFS (see Section 3.2.1.2) by central review will be summarized descriptively and graphically using Kaplan Meier methods. The Kaplan Meier survival estimates, together with the number of subjects, percentage of subjects to experience the event, and the number and percentage of subjects censored will be summarized by treatment group. If data warrant, the Kaplan-Meier estimate for the median progression free survival time and the first and third quartiles will be determined along with 95% CIs using the Brookmeyer-Crowley method. For the analysis of PFS, the PD assessment by central review will be used to determine the status and date of events for PFS regardless of treatment discontinuation.

[name] S.A	
Protocol RI-01-006	Statistical Analysis Plan

A by-subject listing will be provided for central review as well as investigator assessed PFS by treatment group.

Table 11 provides the detailed event/censoring rules for statistical analysis of PFS.

 Table 11 Event/Censoring Rules for PFS Analysis

Situation	Date	Outcome
No baseline tumor assessment	Date of randomization	Censored
PD or death at or before next scheduled assessment	Date of the first radiological tumor assessment demonstrating PD, or date of death	Progressed
New anticancer treatment started without documented PD	Date of last radiological tumor assessment prior to initiation of new therapy	Censored
PD or death after more than one missing assessments	Date of the last radiological tumor assessment prior to the missing assessments	Censored
No PD and no death	Date of the last radiological tumor assessment	Censored
Death before first PD assessment	Date of death	Progressed
Death between adequate assessment visits	Date of death	Progressed

For the Week 28 CSR analysis, subjects will be administratively censored at Week 28 if no progression or other censoring appeared prior to Week 28.

4.10.3.2 Analysis of Overall Response by Central Review at Week 12 and at Week 28

OR by central review at Week 12 and at Week 28 will be summarized using frequencies, percentages and corresponding 95% CIs by treatment group.

4.10.3.3 Analysis of Complete Response by Central Review at Week 28

Complete response (CR) by central review at Week 28 will be summarized using frequency, percentage and corresponding 95% CI by treatment group.

4.10.3.4 Analysis of Complete Response by Central Review up to Week 28

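### ORR and CR at Week 28 are assigned to ITT but computed on subjects with a Week 28 response, so some subjects withdrawn for early progression can leave the denominator

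*SAP*

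**What the plan says.** **Analysis set and denominator.** SAP 4.10.3 says of the secondary efficacy endpoints that "they will be analyzed for the ITT Analysis Set". Three general rules then apply:

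- SAP 4.10.1.3, after dealing with the primary endpoint: "Analysis and descriptive summaries for other endpoints will be based on available observed data".
- SAP 4.2.2 defines the percentage denominator as "the total number of subjects providing data at the relevant time point".
- Protocol 9.1.2: "Other missing values will not be imputed, unless otherwise specified in each analysis section".

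The endpoint sections do not override them. SAP 4.10.3.2 says only that "OR by central review at Week 12 and at Week 28 will be summarized using frequencies, percentages and corresponding 95% CIs by treatment group", and SAP 4.10.3.3 does the same for CR at Week 28. The definitions in SAP 3.2.1.2 give no missing-response rule for either endpoint. For CR as best response they do borrow the primary derivation.

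**Scans after stopping drug.** Protocol 7.2 says that subjects who progress ("per Investigator assessment) are expected to be withdrawn from study drug") attend the ET Visit and are then followed by telephone. Protocol 4.5 fixes the timing: "Subjects experiencing disease progression will discontinue study drug and attend the ET Visit, which is to be scheduled 8 weeks after the last dose". Protocol 8.1.2 keeps the Week 28 scan for the others: "Subjects who have withdrawn from study drug for any reason other than disease progression will also undergo tumour assessment at Week 28".

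**Primary endpoint.** SAP 3.2.1.1 codes SD or PD at Week 12 with Week 28 missing as non-response. It codes a Week 12 response with Week 28 missing as response.

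**Visit windows.** SAP Appendix 5 gives Days 56-112 for Week 12 (target 84) and Days 168-224 for Week 28 (target 196). A note says early-termination scans are assigned by target day.

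**The concern.** Whether a subject has a Week 28 scan depends partly on an earlier outcome. Subjects who stop drug because of progression lose the scheduled scan, while subjects who stop for other reasons keep it. An observed-data denominator then removes some of the subjects most likely to be non-responders at Week 28. The remaining rate is high relative to the ITT label, and the contrast between arms can shift if early progression differs by arm.

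What is at stake is limited but real. SAP 2.2 lists comparison of OR and CR at Week 28 as a secondary objective. The protocol's amendment summary shows that ORR at Week 28 was the primary endpoint before Amendment 4, so readers will set it beside BORR. The same subject could be a non-responder in one table and absent from the next.

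**Working it through.** The documents state no figure for this point, so there is none to reproduce. The check has two parts.

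**1. Where the ET scan falls.** Inputs: ET 56 days after the last dose (Protocol 4.5); dosing windows of ±2 days at Week 4 and ±7 days at Weeks 12 and 20; ET window of ±7 days (Protocol Table 1-1); the scan windows of SAP Appendix 5. Nominal ET day = last dose day + 56. The range adds both windows.

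| Last dose | Nominal ET day | Range | Position |
|---|---|---|---|
| Week 4 (Day 22) | 22 + 56 = 78 | 78 ± 9 = 69-87 | all 19 days in the Week 12 window |
| Week 12 (Day 84) | 84 + 56 = 140 | 140 ± 14 = 126-154 | all 29 days in the gap 113-167 |
| Week 20 (Day 140) | 140 + 56 = 196 | 196 ± 14 = 182-210 | all 29 days in the Week 28 window |

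- Last dose Week 4: the subject is counted at Week 12 and has no later scheduled scan, so Week 28 is missing.
- Last dose Week 12: if the windows are applied strictly, no day maps to Week 28. By nearest target, Days 126-139 (14 days) go to Week 12 and Days 141-154 (14 days) go to Week 28. Day 140 is 56 days from both targets, a tie that the SAP does not resolve.
- Last dose Week 20: nothing is lost.

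**2. Size, on assumed inputs.** If a share m of randomised subjects is excluded and all of them are non-responders, an all-randomised rate p is reported as p/(1 − m). This is an upper bound.

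- p = 88% (the reference rate in SAP 4.10.2.3.4, stated there for BOR and applied here to Week 28 ORR as an assumption): 0.88/0.99 = 88.9%; 0.88/0.97 = 90.7%; 0.88/0.95 = 92.6%.
- p = 60% (the CR + CRu rate in Protocol 2.2.3, used as a stand-in for CR): 60.6%, 61.9% and 63.2% for the same shares.

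Two assumed cases of unequal loss, at 156 per arm (SAP 4.13.2):

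- *Apparent difference.* With 137 responders in each arm, the ITT rates are both 137/156 = 87.8%, difference 0 (90% CI −6.2 to 6.2). Excluding 8 and 2 non-responders gives 137/148 = 92.6% and 137/154 = 89.0%, difference +3.6 points (90% CI −2.0 to 9.3).
- *Masked difference.* With 130 and 137 responders, the ITT rates are 83.3% and 87.8%, difference −4.5 points. Excluding 12 and 4 gives 130/144 = 90.3% and 137/152 = 90.1%, difference +0.1 points.

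The intervals use the asymptotic score (Miettinen-Nurminen) method as an approximation to the SAP's exact score method.

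**The case against.** **Size.** Protocol 4.3 describes a slow-growing disease, and no passage gives a rate of progression by Week 12 on rituximab. The 8-versus-2 case is constructed: it removes 8/19 = 42% of one arm's non-responders and 2/19 = 11% of the other's. Even then the 90% CI includes zero and lies within ±17 points. This stands. The examples show direction and scale per excluded subject, not an expected effect.

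**Visibility.** SAP 4.2.2 reports n, so a reader can see the denominator shrink and can divide by the number randomised. SAP 4.6.1.3 tabulates completion of Weeks 12 and 28 and reasons for discontinuation by arm, and SAP 4.12.3 tabulates COVID-19 visit impact. This stands in part: none of these tables is specific to a missing Week 28 response.

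**Certainty.** A reader might infer that the Week 28 rates are biased upward as a matter of fact. The documents do not support that. Withdrawal follows investigator-assessed progression, the response is read centrally, and the two can differ, so not every excluded subject is a certain non-responder. Protocol 8.2 leaves response-assessment details to the imaging charter, which is not available here. If the charter carries central PD forward to Week 28, the SAP does not say so.

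**Consistency.** A reader might also infer that counting every missing Week 28 response as failure simply matches the primary analysis. It does not: SAP 3.2.1.1 keeps a Week 12 responder with a missing Week 28 scan as a responder. Only the rule for prior central PD or death follows directly from the argument above. Other missing responses need a stated choice.

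**Conclusion.** The concern holds in conditional form. Read together, the SAP rules allow subjects withdrawn for progression after the Week 4 dose, and some or all of those whose last dose is at Week 12, to leave the Week 28 ORR and CR denominators despite the ITT label. To the extent that they are non-responders, both rates are inflated. The contrast between arms can be distorted in either direction if early progression differs by arm.

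The size is unknown and may be small. On the assumed shares above, the upper bound at 88% is about 1 to 5 points. It rests on two assumptions: the excluded share, and that all excluded subjects are non-responders.

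A reader might take this as a threat to the equivalence conclusion. It is not one. Week 28 ORR and CR are descriptive, with no margin or decision rule. BORR and best CR use their own derivation, and PFS counts progression directly. No outcome-dependent loss is shown for ORR at Week 12. The change is worth making because it is cheap and corrects a stated rule.

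**What to change.** In SAP 4.10.3.2 and 4.10.3.3, for ORR and CR at Week 28:

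1. Exempt these endpoints from SAP 4.10.1.3 and 4.2.2, and use all ITT subjects as the denominator.
2. Count centrally documented PD or death before or at Week 28 as non-response at Week 28.
3. For other missing Week 28 responses, including those due to COVID-19, report non-response as the main summary and observed-case as sensitivity. State that this fixed-time rule differs from BORR for Week 12 responders with a missing Week 28 scan.
4. Show the number of missing Week 28 responses by arm and reason (prior PD, death, COVID-19, other).
5. In Appendix 5, state how ET scans on Days 113-167 are assigned, including the Day 140 tie.

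The cost is SAP wording and a few tables; no new data are needed. Reported rates fall slightly, and dropouts who were responding count as non-responders in the main summary. If responses are missing at random in both arms, a true difference shrinks by the missing share. With 5% missing, 88% vs 80% (8.0 points) becomes 0.95 × 88 = 83.6% vs 0.95 × 80 = 76.0% (7.6 points). The observed-case summary makes this visible.

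Descriptive between-arm differences with CIs would be an optional extra and are not part of this correction.
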